## 10.2 Secondary endpoints

1. Changes in lung compliance (defined as tidal volume / (peak inspiratory pressure – PEEP)) from baseline and absolute values at day 5 (96 hrs  $\pm 2$  hrs), day 7 (144 hrs  $\pm 4$  hrs), end of treatment, 3 and 5 days post end of treatment

2. Clinical status as assessed by a 7-point WHO ordinal scale at baseline and daily up to 5 days post end of treatment and at day 28, discharge or death (whichever comes first).
3. Mean daily Sequential Organ Failure Assessment (SOFA) score at baseline through to 5 days post end of treatment
4. In follow up period, number of oxygenation free days, ventilator free days, intensive care stay, up to 28 days or death or discharge, whichever occurs first.
5. Incidence and number of days of new oxygen use, non-invasive ventilation or high flow oxygen devices in the first 28 days.
6. Incidence and number of days of new mechanical ventilation use during in the first 28 days
7. In hospital mortality

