### 3.2 Secondary Objectives

1. Investigate the impact on patient's clinical status over time using the WHO ordinal scale of clinical improvement.

2. Investigate the effect of nebulised rtPA on other respiratory markers (such as lung compliance) and organ dysfunction
3. Investigate the impact on in hospital mortality and resource utilisation

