### 7.3 Treatment Schedule for nebulisation

Patients in the rtPA and SOC group will receive the first dose as soon as possible after enrolment, and in accordance with the dosing schedule below. The time of initiation of the first dose will be recorded and the timing of the initiation of subsequent doses will be relative to this time. 10mg rtPA will be administered by nebulisation every 6 hours. Treatment with rtPA will be administered at a dose of 10 mg every 6hrs for a minimum of 5 days initially and a maximum of 14 treatment days overall.

#### 7.3.1 Cohort 1

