The following tests are to be done daily until 5 days after the last dose (day 7 for SOC patients), and then weekly (+/- 1 day) until day 28, discharge or death whichever occurs first:

- Directed physical examination at baseline, and thereafter weekly only in cohort 2
- vital signs (heart rate, temperature, blood pressure)
- Concomitant medications
- Review of Adverse events and Adverse drug reactions including bleeding episodes

The following assessments are to be done daily until 5 days after the last dose (day 7 for SOC patients) after the baseline assessments were done for these tests:

- Clinical status as assessed by a 7-point ordinal scale
- SOFA score
- Glasgow coma scale

The following end of study data will also be collected at day 28, discharge or death whichever occurs first:

- Documentation of any Oxygenation free days in the first 28 days
- Documentation of any Ventilator-free days in the first 28 days
- Incidence and duration of new oxygen use, non-invasive ventilation or high flow oxygen devices in the first 28 days.
- Documentation of incidence and duration of new mechanical ventilation use during the trial
  - Documentation of intensive care unit (ICU) free days in the first 28 days Death and cause of death (if applicable)
  - Documentation of any Oxygenation free days
  - Documentation of any Ventilator free days
- At 28 days on trial (or death or discharge, whichever comes first), a single measurement will be taken on the 7-point ordinal scale (see section 7.74)

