### **7.5.2 Cohort 1 -Data collection for matched historical controls**

The following data will be collected for matched historical controls:

- Method of COVID-19 confirmation (PCR or radiological)
- Matching criteria (type of oxygen support, age, severity of disease according to  $\text{PaO}_2/\text{FiO}_2$  ratio, ethnicity, gender)
- COVID-19 admission history – to include PCR and CXR findings, date of admission to hospital, date of ICU admission, date of oxygen support and the progression of oxygen support to death or discharge from the study, presence or absence of pulmonary embolism and deep vein thrombosis. Presence of haemophagocytic syndrome will also be recorded, as this impacts on fibrinogen levels.
- Date of admission to hospital and duration of stay
- $\text{PaO}_2$

- $\text{FiO}_2$
- Patient position
- Ongoing 7-point ordinal scale
- Medical history – medical history to be reviewed and relevant history as assessed by the clinician to be recorded in the CRF, including an ISARIC style categorisation for all the major organ systems
- Concomitant medications
- SOFA score
- Glasgow coma scale
- Local blood results as per section 7.6.2
- Results from other standard of care assessments may also be collected if they explain the rate of change for the  $\text{PaO}_2/\text{FiO}_2$  ratio, such as secondary infections, medication changes.

This data will be collected where available for 28 days from the date of admission to hospital.

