### **10.6.3 Secondary outcome analysis**

All secondary outcomes measured overtime will be summarised at each post-baseline timepoint, for each group, and overall where appropriate:

- Clinical status as assessed by a 7-point ordinal scale and change in clinical status
- Changes in lung compliance (computed in the database using tidal volume / (peak inspiratory pressure – PEEP)) from baseline and absolute values at day 5 (96 hrs ± 2 hrs), day 7 (144 hrs ± 4hrs), end of treatment, 3 and 5 days post end of treatment.
- The Mean daily Sequential Organ Failure Assessment (SOFA) score and change from baseline

The following secondary outcomes will also be summarised for each group, and overall, where appropriate:

- The number of oxygenation free days in the first 28 days
- Number of ventilator-free days in the first 28 days
- The incidence and number of days of new oxygen use, non-invasive ventilation or high flow oxygen devices in the first 28 days.
- Incidence and number of days of new mechanical ventilation use during the trial
- Intensive care unit (ICU) free days in the first 28 days
- In hospital mortality
- Length of ICU stay post treatment
- Length of ventilation
- Use of vasopressors

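### Oxygen-free and ventilator-free days are defined to stop at discharge or death, with no start day, death score or discharge credit, so going home sooner can lower the score

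*Protocol*

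**What the plan says.** Item 4 of Protocol 10.2 asks for the "number of oxygenation free days, ventilator free days, intensive care stay, up to 28 days or death or discharge, whichever occurs first". The synopsis and SAP 5.2 carry the same words. In all three places the item opens by placing the count in the follow-up period, a term that neither document defines.

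Two other protocol sections are worded differently. In 7.5.1 the header reads "The following end of study data will also be collected at day 28, discharge or death whichever occurs first", and one of the items beneath it is "Documentation of any Ventilator-free days in the first 28 days". Section 10.6.3 lists "Number of ventilator-free days in the first 28 days" and "Intensive care unit (ICU) free days in the first 28 days". It also lists length of ICU stay after treatment, as does SAP 5.2. ICU-free days are therefore an additional summary and do not replace the stay named in 10.2.

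On timing, Protocol 7.3 sets a clock from the first dose, but for dosing: "the timing of the initiation of subsequent doses will be relative to this time". The synopsis runs participation from informed consent, and 4.1 speaks of follow-up from the end of the treatment phase. For the cohort 1 historical controls, 7.5.2 says: "This data will be collected where available for 28 days from the date of admission to hospital".

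These outcomes serve the third secondary objective, "Investigate the impact on in hospital mortality and resource utilisation". SAP 6.4 summarises them by group. SAP 6.1 rules out adjustment for missing data. No passage gives a score for death or credits days after discharge.

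**The concern.** A free-day count is meant to rise with benefit. One that stops at discharge gives nothing for days at home, so a patient who recovers and leaves early scores less than one with the same recovery who stays. One that stops at death without a death score keeps whatever support-free days came first. A group with shorter stays and fewer deaths could then show the lower mean.

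The distortion is plainest in the non-invasive group. A patient never ventilated there has a ventilator-free count equal to the days in hospital within the window. Cohort 2 plans at least 10 such patients. In cohort 1 the outcome is set beside that of historical controls, who were added so that efficacy could inform the size of a later trial (Protocol 2.5).

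**Working it through.** The documents give no free-day figure to reproduce, so the check applies the definition to example courses. All courses are assumptions, and days are counted from day 1.

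**Formulas.** Let v be the last supported day, with support continuous to v and none afterwards.
- As 10.2 is written: score = min(28, day of discharge, day of death) − v.
- Fixed window: score = 28 − v if alive, 0 if dead in hospital by day 28.

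**Single patients.**

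| Course | Rule | Home day 8 | In hospital to day 28 | Dead day 20 |
|---|---|---|---|---|
| Last ventilated day 5 | as written | 8 − 5 = 3 | 28 − 5 = 23 | 20 − 5 = 15 |
| | fixed | 23 | 23 | 0 |
| Never ventilated (v = 0) | as written | 8 | 28 | 20 |
| | fixed | 28 | 28 | 0 |
| Last oxygen day 7 | as written | 8 − 7 = 1 | 28 − 7 = 21 | 20 − 7 = 13 |
| | fixed, home without oxygen | 21 | 21 | 0 |

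For equal v, a death on day d outscores going home on day h whenever d > h and the patient who died had stayed off support after v. A patient supported from day 1 until death scores 0 under both rules.

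**Start day.** If counting began only after day 7, with day 28 kept as the end, the first row would become 1, 21, 13. The values move but the order does not.

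**Group example, discharge timing only.** Every death is on the ventilator and scores 0 under both rules. Survivors were last ventilated on day 5. Group A has 25% mortality and survivors go home on day 12; group B has 50% and day 24.
- As written: A = 0.75 × (12 − 5) = 5.25; B = 0.50 × (24 − 5) = 9.5.
- Fixed: A = 0.75 × 23 = 17.25; B = 0.50 × 23 = 11.5.

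The order reverses. In general, A scores below B as written when (1 − mA)(hA − 5) < (1 − mB)(hB − 5), where m is mortality and h the survivors' discharge day. With mA = 25%:

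| Mortality in B | B home day 20 | B home day 24 | B home day 28 |
|---|---|---|---|
| 50% | hA < 15 (to day 14) | hA < 17.67 (to day 17) | hA < 20.33 (to day 20) |
| 60% | hA < 13 (to day 12) | hA < 15.13 (to day 15) | hA < 17.27 (to day 17) |

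**Group example in which deaths are also credited.** Ten never-ventilated patients per group.
- 9 home on day 8 and 1 dead on day 20: as written (9 × 8 + 20)/10 = 9.2; fixed (9 × 28)/10 = 25.2.
- 8 home on day 14 and 2 dead on day 20: as written (8 × 14 + 2 × 20)/10 = 15.2; fixed (8 × 28)/10 = 22.4.

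The group with faster discharge and fewer deaths looks worse as written and better under the fixed rule.

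**The case against.** The strongest reply is that the analysis section (10.6.3) and 7.5.1 refer to the first 28 days with no stop in the item itself, and that the cohort 2 derivation is left to a SAP still to be written. A reader might infer from 10.2 that truncation is settled everywhere. It is not: it is explicit in three places and unreconciled in two. The reply does not remove the problem. The 7.5.1 items sit under a header that collects them at the earliest of day 28, discharge or death, and a literal 28-day count would still leave death unscored. A never-ventilated patient dead on day 20 could then count 28.

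Other tempting inferences go too far.
- That first dose is the agreed start for treated patients, leaving only the controls open. The sentence in 7.3 governs dosing, and the follow-up period is undefined for everyone. The size of any misalignment with the controls cannot be derived.
- That the protocol predicts 25% against 50% mortality between groups. Section 2.1 gives 25–60% for ARDS in general under standard care, and 4.1 gives 50% for patients on IMV. The pairing is an assumption.
- That deaths often outscore recoveries. No passage says how often patients spend long off support before dying in hospital.

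The point about small consequences stands. Cohort 1 treated nine patients, cohort 2 has no comparator, nothing is powered, all data are listed, and mortality, length of ventilation and ICU stay are shown separately. Separate mortality tables do not, however, correct the penalty for early discharge.

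**Conclusion.** The concern holds for oxygenation-free and ventilator-free days as defined in the synopsis, 10.2 and SAP 5.2. Followed as written, the measure can run against benefit: each day of earlier discharge off support costs one day of score, and support-free days before an in-hospital death are kept. The competing 28-day wording needs reconciling and supplies neither missing rule. The direction follows from the definition alone; the sizes shown rest on the assumed courses, the assumed mortality contrast and counting from day 1.

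This should be corrected, but it does not undermine the trial. A reader might take it to invalidate the efficacy assessment. It does not, because the primary efficacy outcome is the oxygenation ratio and these counts are descriptive.

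**What to change.** Use one definition in the synopsis, 7.5.1, 10.2, 10.6.3 and the cohort 2 SAP:
1. A stated start day, for example first dose, and a fixed 28-day window.
2. Days after discharge alive count as free; for oxygen, only if discharged without it.
3. Death by day 28 scores 0, or follows another rule stated in advance.
4. The same rule for ICU-free days.
5. In-hospital mortality shown beside the counts.

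The SAP should say that crediting days after discharge is part of the endpoint definition, so that it does not collide with a statement such as that in SAP 6.1 on missing data.

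For cohort 1 the SAP is already at version 1.0 and preliminary data have been reviewed. Add the new count there as a labelled post-hoc analysis beside the count now specified, documented and justified as SAP 2.1 requires. State the control start day, and how the window applies to re-treated patients whose participation may exceed 28 days (7.3.5).

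The cost for cohort 2 is wording and one derivation before lock. There are three downsides.
- Follow-up ends at discharge, so the rule assumes no death, readmission or restart of support between discharge and day 28.
- The ordinal scale in 7.7.4 has no explicit level for discharge on oxygen, so a yes/no item at discharge may be needed.
- If a control's matched baseline falls b days after admission, only 28 − b days remain in the extracted data. Longer extraction depends on the data notice in 6.4, due to end on 31 March 2021.

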### **10.3 Exploratory endpoints**

Change in levels of plasma biomarkers of pro- and anti-inflammatory markers (e.g. interleukin-6, interleukin-8, interleukin-10 and interleukin-1Ra), endothelial injury (plasma von Willebrand factor) coagulation (procogulants, anticoagulants, and fibrinolytic pathway) measure of tissue damage.

Historical controls will not provide data for exploratory endpoints.

### **10.4 Sample size and recruitment**

#### **10.4.1 Sample size calculation**

The sample size for this pilot study is not based on a statistical consideration. The recruitment target of 12 patients treated with rtPA and SOC is based on feasibility and the planned recruitment rate.

Similarly, for cohort 2 the sample size of 30 patients is not based on statistical consideration, but has been selected on the grounds of what is reasonable amid a second surge of COVID-19 admissions in early 2021 and the number of patients we might reasonably accept to recruit across the 2 sites over the next 2 to 6 weeks.

#### **10.4.2 Historical control recruitment – Cohort 1 only**

Historical controls will be recruited at a ratio of 2 controls to every 1 rtPA + SOC arm patient, and will be matched according to the following characteristics:

1. Ventilation and oxygen type (IMV and non-invasive oxygen support)
2. Severity as determined by  $\text{PaO}_2/\text{FiO}_2$  ratio
3. Gender
4. Age (+/- 2 years, up to a maximum of 10 years)
5. Ethnicity

Matching will be done in the order that the characteristics are presented above.

Deceased patients can be considered for matching as controls. However, as a certain number of observations are required for developing a P/F ratio of the curve, patients who died within 48 hrs of admission are excluded.

Baseline data during admission will be used for matching.

An age range of +/- two years was used in the first instance, and this was widened until two eligible patients were identified that matched the treatment patient's ethnicity, up to a maximum of +/- 10 years.

Where more than two controls are identified, two controls will be drawn at random without replacement among all considered historical patients that match according to the characteristics above.

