### **10.6.2 Primary outcome analysis**

The PaO2/FiO2 ratio measured over time will be described for each group. The change from baseline in the PaO2/FiO2 ratio will be summarised at each post baseline timepoint. Plots will be used, where appropriate, to show the PaO2/FiO2 summarised for patients over time.

PaO2/FiO2 will be a calculated field on the trial database derived from the fields for PaO2 and FiO2. For cohort 2 data will be extracted once a day coinciding with the worst PF ratio. As PF ratio is the primary endpoint, in addition to the worst PF ratio, up to a maximum of 6 data points spread across 24 hrs that represents patients clinical status will be extracted. Details of further data derivation and analyses will be described in the SAP.

All patient data will be used, regardless of any intercurrent events that may have occurred after enrolment:

- Data from patients recruited into the rtPA + SOC group will be summarised whether or not patients have received all planned doses of the IMP.
- Any change in requirement for oxygenation and ventilation support will be summarised and described
- Changes in PaO2/FiO2 ratio over time will be described and interpreted taking into consideration that a patient's condition may have changed and led to their ventilation type changed post enrolment. If data allows, additional descriptions of the PaO2/FiO2 ratio over time may be performed in each subgroup of patients experiencing such changes (e.g. IMV to NIV, or vice versa).

The incidence and severity of bleeding events will be summarised in each group, and the change in fibrinogen levels will also be summarised at each post-baseline timepoint.

For cohort 1, subject to the final sample size and data quality, outcomes will also be compared between the SOC only group and intervention (rtPA + SOC) group using appropriate regression methods to make adjustment for baseline characteristics. Appropriate data transformations required for model assumptions will be considered if necessary.

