Primary Outcomes	
Efficacy
 
 1. Change in $\text{PaO}_2/\text{FiO}_2$ ratio from baseline (defined as 3 days prior to treatment), daily during treatment, end of treatment and 3 and 5 days post treatment in the groups receiving rtPA 
Safety
 
 1. Incidence and severity of major bleeding events directly attributable to the study drug 2. Decrease in fibrinogen levels to $< 1.5 \text{ gm/L}$ during treatment period and 48 hrs after the last dose of treatment 3. Number and nature of serious adverse events causally related to the treatment
Population	
Inclusion criteria
 
 1. Patients with COVID-19 confirmed by PCR 2. ≥ 16 years 3. Willing and able to provide written informed consent or where patient doesn't have capacity, consent obtained from a legal representative 4. Patients on IMV must meet both the following criteria: 
 a. $\text{PaO}_2/\text{FiO}_2 \leq 300$ b. Intubated > 6 hrs 5. Patients on NIV must meet all the following criteria: 
 a. $\text{PaO}_2/\text{FiO}_2 \leq 300$ or equivalent imputed by non-linear calculation from $\text{SpO}_2/\text{FiO}_2$ b. In-patient > 6 hours and being actively treated

	
c. On support with non-invasive ventilation OR continuous positive airway pressure (CPAP) OR high flow OR standard oxygen therapy.
 
Exclusion criteria
 
 1. Females who are pregnant 2. Concurrent involvement in another experimental investigational medicinal product 3. Known allergies to the IMP or excipients of IMP 4. A pre-existing bleeding disorder (e.g. severe haemophilia) 5. Pre-existing severe cardiopulmonary disease (e.g. incurable lung cancer, severe chronic obstructive lung disease, cardiomyopathy, heart failure or impaired contractility <estimated 40% LVEF or RVEF) 6. Fibrinogen < 2.0 g/L at time of screening 7. Patients considered inappropriate for critical care (prior decision re ceiling of care established) 8. Patients with active bleeding in the preceding 7 days 9. Patients who in the opinion of the investigator are not suitable.
Sample size	36: 12 participants receiving rtPA + standard of care (SOC), and 24 matched historical controls receiving SOC only.
Randomisation	Not applicable – study is open label.
Sponsor protocol number	132151
Funder (s):	Royal Free Charity
EudraCT No	2020-001640-26

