3.3 Exploratory objective

Changes to coagulation and inflammatory markers concerning intervention and response to treatment.

4 Trial Design

This study is a phase II, open label, multicentre, uncontrolled, repeated dose, pilot trial of nebulised rt-PA in patients with COVID-19 ARDS.

The study will recruit patients requiring either IMV or non-invasive oxygen support. Eligible patients (or if patients lack capacity, their legal representative) will be provided with an information sheet and informed consent will be sought. Eligibility will be assessed via routine clinical assessments, which may have been done prior to consent. The only exceptions are a pregnancy test (blood or urine), and possibly any assessments that were not done as per routine care. These must be done following consent, and all screening assessments must have been done during the 24-hour period before dosing with rtPA. Patients will be followed up until discharge, death, or day 28 whichever is sooner.

The study will recruit historical controls at a ratio of 2 controls to every 1 rtPA + SOC arm patient, and will be matched according to the following characteristics:

1. Ventilation and oxygen type (IMV and non-invasive oxygen support)
2. Severity as determined by $\text{PaO}_2/\text{FiO}_2$ ratio
3. Gender
4. Age (+/- 2 years, up to a maximum of +/- 10 years)
5. Ethnicity

Matching will be done in the order that the characteristics are presented above.

Deceased patients can be considered for matching as controls. However, as a certain number of observations are required for developing a $\text{PaO}_2/\text{FiO}_2$ ratio of the curve, patients who died within 2 to 3 days of admission are excluded.

For characteristics 1 and 2, baseline data during admission will be used for matching.

An age range of +/- 2 years was used in the first instance, and this was widened until two eligible patients were identified that matched the treatment patient's ethnicity, up to a maximum of +/- 10 years.

Where more than two controls are identified, two controls will be drawn at random without replacement among all considered historical patients that match the age, gender and severity the case.

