6.1 General statistical considerations

All analyses will be descriptive in nature and should be considered as hypothesis generating rather than providing firm conclusions. All statistical tests and confidence intervals will be 2-sided. Significance will be considered at the 5% level and confidence intervals will be at the 95% level.

Analyses for both primary and secondary outcomes will be conducted following an Intention To Treat (ITT) approach, and non-compliance will be reported at the individual patient level. No adjustments for missing data will be made.

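### Historical controls are selected on early death, by rules that differ between protocol and SAP and run on a clock not tied to the matched case's first dose

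*Protocol*

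**What the plan says.** Protocol 10.4.2 allows deceased patients as controls but adds that "patients who died within 48 hrs of admission are excluded". The reason given is practical: "as a certain number of observations are required for developing a P/F ratio of the curve". SAP section 4 gives the same reason but a different limit: "patients who died within 2 to 3 days of admission are excluded". The SAP cites protocol version 7.0. The version history for 8.0 to 10.0 records no change to control selection.

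Nothing comparable is written for treated patients. Their entry conditions (SAP section 1; also protocol 6.1.1) are "Intubated > 6 hrs" for ventilated patients and "In-patient > 6 hours and being actively treated" for the others. After enrolment, protocol 10.6.2 states: "All patient data will be used, regardless of any intercurrent events that may have occurred after enrolment". SAP 6.1 agrees: "Analyses for both primary and secondary outcomes will be conducted following an Intention To Treat (ITT) approach".

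The two groups run on different clocks. Control data cover 28 days from hospital admission (protocol 7.5.2, SAP 5.5). The rtPA patient's participation runs from consent to day 28, discharge or death (protocol section 1). The control's baseline is placed before enrolment by a reference to section 8.2 (protocol 10.6.1, SAP 6.2), but protocol 8.2 is about recording adverse events.

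In-hospital mortality is a secondary endpoint (protocol 10.2), and death is the worst category of the ordinal scale (7.7.4).

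**The concern.** A control should be someone who could have been the treated patient at the moment treatment began. This rule asks something else: that the control survived a fixed time from admission, whatever the case's own time to first dose.

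Two errors follow, in opposite directions. For a case dosed before the cut-off, controls who died between that lag and the cut-off are removed, although the case would have been kept after dying in the same interval. That makes the controls look better. For a case dosed after the cut-off, a control who died between the cut-off and the case's lag stays in, although the case had to be alive throughout. That makes rtPA look better. Adjusting for baseline PaO2/FiO2, the only covariate in the SAP model, removes neither error.

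These controls are the only comparator in the trial. Protocol 2.5 says they were recruited to evaluate efficacy so that a larger phase 3 study could be sized, and the DMC is to advise on an RCT from the results. A distortion in control mortality or ordinal status would carry into those planning figures.

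**Working it through.** **Plan's own figure.** There is no power calculation to reproduce (10.4.1). The 2:1 ratio does reproduce: 2 × 12 = 24 controls planned and 2 × 9 = 18 obtained (4.1). With 6 ventilated and 3 non-invasive cases, that is 12 and 6 controls.

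**Inputs.** Mortality m: 50% for ventilated patients (10.5), and 25–60% for ARDS generally (2.1). Two inputs are not in the documents: the share f of control deaths that fall inside the window (assumed, up to 30%) and the cohort 1 times from admission to first dose.

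**Step 1: the exclusion taken alone.** If a fraction e of otherwise eligible controls die inside the window, observed mortality is (m − e)/(1 − e).

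With m = 50% by day 28 and constant hazard, e = 1 − 0.5^(d/28) for a window of d days:

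| Window | e | Observed mortality | Shift |
|---|---|---|---|
| 2 days | 4.8% | 47.5% | −2.5 points |
| 3 days | 7.2% | 46.1% | −3.9 points |

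The ambiguity in the SAP wording is therefore worth about 1.4 points on its own.

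**Step 2: deaths concentrated early.** Put e = f × m:

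| m | f = 10% | f = 20% | f = 30% |
|---|---|---|---|
| 25% | 23.1% (−1.9) | 21.1% (−3.9) | 18.9% (−6.1) |
| 50% | 47.4% (−2.6) | 44.4% (−5.6) | 41.2% (−8.8) |
| 60% | 57.4% (−2.6) | 54.5% (−5.5) | 51.2% (−8.8) |

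At m = 50% and f = 30%, expected deaths among the 12 ventilated controls fall from 6.0 to 4.9.

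**Step 3: the opposing effect.** Under the same constant hazard, a control who had to be alive at the case's lag of L days has mortality to day 28 from admission of 1 − 0.5^((28 − L)/28). Two hypothetical lags show how the sign turns:

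- L = 0.25 days (the 6-hour floor, for a patient dosed 6 hours after admission): 49.7%. The 48 h rule gives 47.5%, which is 2.2 points too low and flatters controls.
- L = 6 days: 42.0%. The 48 h rule still gives 47.5%, which is 5.5 points too high and flatters rtPA.

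The two agree only when the lag equals the cut-off.

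**Step 4: scale.** The approximate 95% half-width of a mortality difference at 50% is 1.96 × √(0.25/9 + 0.25/18) = 40 points for 9 v 18. For 6 v 12 it is 1.96 × √(0.25/6 + 0.25/12) = 49 points.

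**Step 5: the PaO2/FiO2 regression.** The model in SAP 6.3 takes the value at end of treatment as its outcome, and SAP 6.1 says "No adjustments for missing data will be made". A control who died within two or three days would probably have no such value and would drop out of the model anyway. The exclusion therefore bears mainly on mortality, the ordinal scale and the early PaO2/FiO2 summaries. Its effect on those PaO2/FiO2 summaries cannot be sized, because the documents give no standard deviation and no values for early deaths.

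**The case against.** The strongest reply is that treated patients also had to survive to treatment. The 6-hour condition is a floor and not a typical time. Protocol 6.3 would ideally leave 24 hours between giving the study documents and seeking consent, though it allows less. The cohort 1 baseline draws on the three days before dosing, where data exist. If every case was first dosed at least 48 hours after admission, none could have died in the excluded window, and the rule would partly mirror a selection that treatment itself imposed. This stands, and it is why a net direction cannot be claimed.

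It is also fair that the shift is far smaller than sampling error, that the SAP only summarises mortality by group (6.4), that the protocol's regression comparison is conditional on sample size and data quality (10.6.2), and that both documents call the analyses descriptive and hypothesis generating. These points lower the grade. They do not reconcile two different rules, and small numbers do not remove a systematic error in the only comparator.

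The practical reason for the exclusion is weak for mortality and ordinal status, neither of which needs a PaO2/FiO2 curve.

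A reader might go further and infer that the comparison is shown to be biased against rtPA, with the Step 1 and 2 figures as its size. The documents do not support that. Those figures cover one direction only, rest on an assumed early-death share, and in the 50% case apply a figure quoted for ventilated patients to controls in general.

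**Conclusion.** The point holds as a flaw in control selection and as a conflict between the documents. The two exclusion rules differ, the SAP's cannot be applied as written, and neither is tied to the case's time of first dose.

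Taken alone, the exclusion lowers observed control mortality by about 2.5 points (48 h) or 3.9 points (72 h), given 50% 28-day mortality and constant hazard, and by up to about 9 points if 30% of deaths fall in the window. Late-dosed cases push the other way, so the net sign is unknown until the admission-to-dose times are examined. Against a half-width of about 40 points, the effect would not by itself change the reading of a 9 v 18 comparison.

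It would also be too much to infer that the end-of-treatment PaO2/FiO2 regression is materially distorted by this rule. It is probably little affected. Grade: should fix.

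**What to change.** **Rule.** State one identical rule in protocol 10.4.2 and SAP section 4: a control must be alive, in hospital and on the case's support type at the case's own time from admission to first dose, with no later survival condition. Use that same index time for the control's baseline (protocol 10.6.1, SAP 6.2) and follow-up clock (protocol 7.5.2, SAP 5.5). Otherwise time zero stays misaligned.

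**Controls already chosen.** Keep the 18 for the main summary. A full redraw would be post hoc, since protocol 2.5 already describes a preliminary review of cohort 1. Report how many candidates the early-death rule removed, and how many chosen controls fail the index-time rule. Add a sensitivity analysis of mortality and ordinal status that applies the index-time rule and restores eligible early deaths.

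**Cost.** This takes more than a wording change: the rule, baseline and clock must be edited in both documents, and some charts re-reviewed. Some restored controls will have short PaO2/FiO2 curves, and some matched sets may end with fewer than two controls. Protocol 6.4 rests access to control data without consent on notices then due to end on 31 March 2021, so the chart review should be planned with that date in mind.
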